**Document History**

Document	Version Date	Summary of Changes
Original protocol	24 June 2015	Not Applicable (N/A)

## **PROTOCOL SUMMARY**

### **Background and Rationale**

Axial Spondyloarthritis (ax SpA) is a chronic disease whose most devastating clinical manifestation is the loss of mobility. The Assessment of SpondyloArthritis international Society (ASAS) recently created a classification system for ax SpA based on whether patients meet clinical criteria or imaging criteria. Patients meeting the ASAS criteria for ax SpA without evidence of sacroiliitis on x-ray are classified as having non-radiographic axial spondyloarthritis (nr-ax SpA). In several recent studies, anti-tumor necrosis factor (TNF) agents, including etanercept (ETN), demonstrated efficacy in patients with nr-ax SpA. However, additional long-term data are needed, and little is known about the effects of etanercept withdrawal in subjects who have achieved a significant clinical response.

In a small trial (ESTHER) of etanercept-treated patients who had achieved an ASAS partial remission after 48 weeks of etanercept treatment, 13 with nr-ax SpA were withdrawn from therapy. The flare rate in year 2 was 69%, and the mean time to flare was 24.4 weeks. Retreatment with etanercept showed an improvement in all clinical (Bath Ankylosing Spondylitis Disease Activity Index [BASDAI], Ankylosing spondylitis Disease Activity Score [ASDAS], C-reactive protein [CRP]) and imaging (magnetic resonance imaging [MRI] sacroiliac joint [SIJ], MRI spine, MRI enthesitis) variables. Only a portion of the subjects re-established remission status (56% ASAS remission; 44% MRI remission; 33% MRI plus ASAS remission).

The proposed study is a followup of this small pilot study that will further our understanding of the benefits and risks of ETN withdrawal in patients who have achieved a significant clinical response. Much is known already from B1801031 about relapse rates of those achieving remission and continuing on ETN, therefore an open-label study estimating the relapse rates in such patients withdrawn from ETN is planned.

### **Objectives and Endpoints**

- The primary objective of this study is to estimate the proportion of subjects who flare within 40 weeks following withdrawal of ETN in subjects who have achieved inactive disease (defined as ASDAS less than 1.3). The key secondary objective is to measure time to flare after withdrawal of ETN.
- The primary endpoint for this study is occurrence of flare within 40 weeks (defined as an ASDAS greater than or equal to 2.1) following withdrawal of ETN. The key secondary endpoint is the time to flare after withdrawal of ETN.

### **Study Design**

This multicenter, open-label, three period study will evaluate withdrawal and retreatment of ETN in subjects with nr-ax SpA who achieved an adequate response, as measured by Ankylosing Spondylitis Disease Activity Score C-Reactive Protein (ASDAS CRP) less than 1.3 (inactive disease) following 24 weeks of treatment. The study is expected to randomize

[figure not shown]

approximately 200 subjects in Period 1, in order to have approximately 96 subjects qualify for Period 2.

Period 1 is an open-label, 24-week period in which all eligible subjects will be enrolled and treated with ETN 50 mg once weekly plus a stable background non-steroidal anti-inflammatory drug (NSAID) at the optimal tolerated anti-inflammatory dosage. The target for this period is therapeutic response defined as achieving ASDAS CRP less than 1.3 at Week 24. Subjects who do not achieve ASDAS CRP less than 1.3 will not enter Period 2 and will complete the study at the Week 28 day follow-up phone call/visit.

Period 2 is a 40-week withdrawal period where subjects will discontinue ETN following the Week 24 dose, yet maintain the background NSAID. If the subject has not flared by the Week 64 visit, their participation in the study is complete. Subjects who flare (defined as an Ankylosing Spondylitis Disease Activity Score Erythrocyte Sedimentation Rate [ASDAS ESR] greater than or equal to 2.1) during Period 2 will enter a retreatment period (Period 3) and receive approximately 12 weekly doses of open-label ETN.

### Study Schematic

†Flare is defined as ASDAS ESR  $\geq 2.1$

\*The follow-up visit is only required 28 days following the last dose of IP. This will occur either at the end of Period 1 (for subjects that don't qualify for Period 2) or at the end of Period 3 (for subjects who flare and require retreatment).

\*\*Subjects who flare at Week 64 will receive 12 weeks of OL ETN and will have their final study visit at Week 76 and their follow-up visit 28 days later.

## **Study Treatments**

For the purposes of this study, investigational product will be defined as ETN. The sponsor will supply ETN. Investigational product will be administered only to subjects who have provided informed consent. Once a subject's participation in the study has ended, ETN will no longer be supplied to the subject by the investigative site and/or sponsor.

## **Statistical Method**

The primary endpoint, the proportion of subjects who flare (ASDAS ESR greater than or equal to 2.1) in Period 2 will be summarized descriptively as the percent with flare with 95% confidence intervals. This estimate will include all subjects who qualify for the retreatment interval and have at least one evaluation after treatment is withdrawn.

For the key secondary endpoint of time to flare, descriptive statistics will include median time to flare and 95% confidence intervals using the Kaplan-Meier approach.

## SCHEDULE OF ACTIVITIES

The schedule of activities table provides an overview of the protocol visits and procedures. Refer to the [STUDY PROCEDURES](#) and [ASSESSMENTS](#) sections of the protocol for detailed information on each procedure and assessment required for compliance with the protocol.

The investigator may schedule visits (unplanned visits) in addition to those listed on the schedule of activities, in order to conduct evaluations or assessments required to protect the well-being of the subject.

Study Interval	Screen	Period 1 Induction						Period 2 Withdrawal						Period 3 Retreatment (If subject flares during Period 2)				Follow-up d 28 Days After Last Dose	Early DC
		BL Day 1	Wk 4	Wk 8	Wk 12	Wk 16	Wk 24	Wk 28 c	Wk 32	Wk 40	Wk 48	Wk 56	Wk 64	Wk R0 e	Wk R4	Wk R8	Wk R12		
Visit Windowa (Days)	-28 to -5		±4	±4	±4	±4	±7	±4	±7	±7	±7	±7	±7	±4	±4	±4	±4		
Visit Identifier	1	2	3	4	5	6	7	8	9	10	11	12	13	R1	R2	R3	R4	14	
Informed Consent	X																		
Review Eligibility Criteria	X	X						X g											
Demographics	X																		
Medical History h	X																		
Chest Radiograph /TB Testing i	X																		
Contraception Check j	X	X	X	X	X	X	X	X	X	X	X	X	X	X	X	X	X	X	X
Safety Assessments																			
Vital Signs	X	X	X	X	X	X	X	X	X	X	X	X	X	X	X	X	X	X	X
Height/Weight	X						X						X				X		X
Physical Exam	X						X						X				X		X
IBD, Psoriasis, Uveitis Assessment		X	X	X	X	X	X	X	X	X	X	X	X	X	X	X	X	X	X
Adverse Events k	X	→	→	→	→	→	→	→	→	→	→	→	→	→	→	→	→	→	→
Laboratory																			
Hematology/Blood Chemistry l	X	X			X		X						X	X			X		X
Urinalysis l	X												X						
Pregnancy Test m	X	X	X	X	X	X	X	X	X	X	X	X	X	X	X	X	X	X	X

Study Interval	Screen	Period 1 Induction						Period 2 Withdrawal						Period 3 Retreatment (If subject flares during Period 2)				Follow-up d	Early DC
Study Week	Screen b	BL Day 1	Wk 4	Wk 8	Wk 12	Wk 16	Wk 24	Wk 28 c	Wk 32	Wk 40	Wk 48	Wk 56	Wk 64	Wk R0 e	Wk R4	Wk R8	Wk R12	28 Days After Last Dose	Early DC f
Visit Window a (Days)	-28 to -5		±4	±4	±4	±4	±7	±4	±7	±7	±7	±7	±7	±4	±4	±4	±4		
Visit Identifier	1	2	3	4	5	6	7	8	9	10	11	12	13	R1	R2	R3	R4	14	
HLA B27	X																		
hsCRP 	X	X	X	X	X	X	X	X	X	X	X	X	X	X	X	X	X		X
ESR 	X	X	X	X	X	X	X	X	X	X	X	X	X	X	X	X	X		X
Banked Specimen Prep D1		X																	
Banked Specimen Prep B1 and Prep R1		X			X		X												X n
Hepatitis B, Hepatitis C Testing	X																		
Imaging																			
SIJ X-ray o	X																		
MRI Spine & SIJ p	X						X				X		X	X q				X	X
Investigational Product																			
Open-Label Treatment Assignment (First dose administered by study personnel)		X																	
Dispense Investigational Product (IP)		X	X	X	X	X								X	X	X			
Collect IP & Accountability r			X	X	X	X	X								X	X	X		X
Dispense IP Diary Card		X	X	X	X	X								X	X	X			
Collect & Review IP Diary Card			X	X	X	X	X								X	X	X		X
Prior/Concomitant Treatments	X	X	→	→	→	→	→	→	→	→	→	→	→	→	→	→	→	→ s	→ s
Efficacy Assessments																			
Joint Assessment t,u		X			X		X		X		X		X	X			X		X
Physician Global Assessment u (PGA)		X	X	X	X	X	X	X	X	X	X	X	X	X	X	X	X		X

Study Interval	Screen	Period 1 Induction						Period 2 Withdrawal						Period 3 Retreatment (If subject flares during Period 2)				Follow-up d	Early DC
Study Week	Screen b	BL Day 1	Wk 4	Wk 8	Wk 12	Wk 16	Wk 24	Wk 28 c	Wk 32	Wk 40	Wk 48	Wk 56	Wk 64	Wk R0 e	Wk R4	Wk R8	Wk R12	28 Days After Last Dose	Early DC f
Visit Window a (Days)	-28 to -5		±4	±4	±4	±4	±7	±4	±7	±7	±7	±7	±7	±4	±4	±4	±4		
Visit Identifier	1	2	3	4	5	6	7	8	9	10	11	12	13	R1	R2	R3	R4	14	
Health Outcome Assessments																			
BASDAI	X	X	X	X	X	X	X	X	X	X	X	X	X	X	X	X	X		X
BASFI		X	X	X	X	X	X	X	X	X	X	X	X	X	X	X	X		X
Subject Assessment of Disease Activity (SADA)	X	X	X	X	X	X	X	X	X	X	X	X	X	X	X	X	X		X
Subject Nocturnal and Total Back Pain VAS		X	X	X	X	X	X	X	X	X	X	X	X	X	X	X	X		X
BAS-G		X			X		X		X		X		X	X			X		X
EQ-5D		X			X		X		X		X		X	X			X		X
SF-36		X			X		X		X		X		X	X			X		X
WPAI		X	X	X	X	X	X	X	X	X	X	X	X	X	X	X	X		X

Abbreviations: BL=baseline; IBD = inflammatory bowel disease, IP = investigational product; TB=tuberculosis; → = ongoing/continuous event; HLA-B27 = human leucocyte antigen B27; hsCRP = high sensitivity c-reactive protein; SIJ = sacroiliac joint; MRI = magnetic resonance imaging; BASDAI = Bath Ankylosing Spondylitis Disease Activity Score; BASFI = Bath Ankylosing Spondylitis Functional Index; BAS-G = Bath Ankylosing Spondylitis Patient Global Assessment Score; EQ-5D = EuroQol EG-5D Health State Profile; SF-36 = 36-Item Short-Form Health Survey; WPAI = Work Productivity and Activity Impairment Questionnaire .

- a. Day relative to start of study treatment (Day 1).
- b. Screening visit should occur within 4 weeks (28 days) of BL visit but no less than 5 days before BL visit. The screening period may be extended up to 42 days if repeat imaging is required or when tuberculosis prophylactic therapy is started during the screening period.
- c. ASDAS CRP will be calculated at the Week 24 visit, which will determine if subjects are eligible to enter Period 2. If the ASDAS CRP is <1.3 at Week 24, subjects will return to the site at Week 28 to continue with the Period 2 procedures. If the Week 24 ASDAS CRP is ≥1.3, the subject should be notified by phone that their participation in the study is complete. A follow-up call will be conducted in place of the Week 28 visit to assess new and ongoing adverse events and medication taken to treat them since the last dose of investigational product.
- d. Follow-up: For subjects who discontinue the study during Period 1, or enter Period 2 and discontinue from the study *before* the Week 28 visit, or subjects who enter Period 3, there will be a follow-up telephone call to assess new and ongoing adverse events and the medications taken to treat them. This call will be approximately 28 days after the last dose of IP. No follow-up is needed if subjects enter Period 2 and do not experience a flare. If required by local regulations, the follow-up visit may be conducted at the study site.

- e. The first visit of the Retreatment period (Period 3) may occur at the same time as a regularly scheduled visit during Period 2 or it may occur as an unscheduled visit.
- f. Early discontinuation: If a subject discontinues from the study prior to the last visit of any period every effort should be made during the early discontinuation visit to perform all procedures, laboratory assessments (including biomarker samples), questionnaires and obtain the MRI.
- g. Subjects must complete Period 1 and achieve ASDAS CRP <1.3 at the Week 24 visit in order to be eligible to enter Period 2.
- h. Medical history evaluation includes: general medical history, disease specific medical history, evaluation of background medication and family medical history.
- i. Chest x-ray and TB testing: local country guidelines should be followed for appropriate screening and prophylaxis in the setting of anti-TNF therapy, including a chest radiograph and objective TB testing, such as purified protein derivative (PPD) or Quantiferon. If the subject is known to be PPD positive, the test need not be repeated if documentation is available to show the subject meets local criteria for anti-TNF therapy and has not had active TB in the last 2 years. If the subject has a documented negative PPD or Quantiferon test within 3 months prior to the screening visit, the test need not be repeated.
- j. Ensure that the subject is using the appropriate contraception as detailed in [Section 4.5](#) of the protocol and document in the source notes.
- k. Adverse Events both serious and non-serious should be recorded on the case report form (CRF) from the first dose of IP through the subject's last visit. In addition, serious adverse events (SAE) must be reported to Pfizer from the time that the subject provides informed consent.
- l. Hematology/Blood chemistry/Urinalysis/hsCRP/ESR: These laboratory tests do not need to be repeated at the baseline visit (Visit 2) if they were completed at the screening visit  $\leq 14$  days before baseline. Should the laboratory results subsequently show that the subject does not meet the inclusion/exclusion criteria and this is confirmed upon retest, the subject must be withdrawn from the study at that time.
- m. Pregnancy Testing: Women of child-bearing potential must have a negative serum pregnancy test at the screening and baseline visit. Additionally they must have a confirmed negative urine pregnancy test prior to the first dose of investigational product at the baseline visit. The pregnancy test(s) may be repeated at the discretion of the investigator if the subject misses a menses, or if the potential of pregnancy is otherwise suspected. Women of this group must be willing to use a highly effective contraceptive method. Pregnancy test may also be repeated as per request of institutional review board (IRB)/ethics committees (ECs) or if required by local regulations.
- n. Collection of the Prep B1 and Prep R1 banked specimens are only completed at this time point if the subject discontinues early during Period 1.
- o. Screening SIJ x-ray is the first imaging procedure that is performed. The reading to assess eligibility is performed by a central imaging vendor. If the SIJ x-ray must be repeated, the screening period may be extended to 6 weeks. Results of historical x-rays of the SIJ that have been obtained within 4 months prior (12 months in Germany only) to the screening visit could be used in lieu of performing screening x-rays. If historical x-rays are used, the original films, or a copy, must be on site and a copy should be sent to the central reader. If the results are considered unevaluable by the central reader, the x-ray must be performed during screening. The central reader must be able to determine the presence of and/or the degree of sacroiliitis. If the results are considered unevaluable by the central reader and the subject is unable to have a repeat x-ray due to the regulations issued by the German Federation of Radiation Council, the subject will be considered a screen failure.
- p. MRI should only be done after eligibility is determined by SIJ x-ray. The MRI is performed during the screening period. If the MRI must be repeated, the screening period may be extended to 6 weeks.
- q. If a subject experiences a flare in <8 weeks since their previous MRI, there is no need to conduct the MRI at the first retreatment visit.
- r. Drug accountability is done at each clinical visit during Period 1 and Period 3 to assess compliance with the protocol dosing regimen.
- s. Record medications taken to treat any new or ongoing adverse events/serious adverse events that occurred since the last study visit.
- t. Joint Assessment includes: Tender and swollen joint count, dactylitis and enthesitis (Maastricht Anklyosing Spondylitis Enthesitis Score [MASSES]) evaluation.
- u. It is recommended that the same qualified personnel complete these assessments at each visit.

## 1. INTRODUCTION

Spondyloarthritis (SpA) is a chronic, inflammatory disease characterized by joint inflammation, enthesitis and certain extra-articular manifestations in organs such as the eyes, skin, and cardiovascular system. It involves preferentially either the axial skeleton (axial SpA) or peripheral joints (peripheral SpA). The etiology of SpA is unknown but may involve the interaction of genetic and environmental factors. It is currently believed that axial SpA begins in the absence of the classic radiographic features which define ankylosing spondylitis (AS). This beginning disease state is referred to as non-radiographic axSpA. Ankylosing Spondylitis can cause permanent structural changes leading to progressive disability impacting the quality of life. It is unknown if treatment of nr-ax SpA will prevent progression to AS, but SpA at all stages represents significant health and socioeconomic burdens for the individual patient and society.

The use of MRI and improved radiographic technology has generated new interest in initiating early intervention and treatment of axial SpA before significant, irreversible damage has occurred. Early diagnosis could potentially lead to earlier intervention with the goal of disease activity control, maintenance of physical function, and optimization of quality of life.

The name, title, address and telephone number(s) of the sponsor's medical expert for the trial document are provided in the study reference manual.

### 1.1. Mechanism of Action/Indication

Etanercept (ETN) is a recombinant human necrosis factor alpha (TNF $\alpha$ ) soluble receptor that blocks TNF $\alpha$  binding to cell surface receptors and initiation of intracellular signaling. ETN is approved for the treatment of AS and nr-ax SpA.

### 1.2. Background and Rationale

Axial Spondyloarthritis (ax SpA) is a chronic disease whose most devastating clinical manifestation is the loss of mobility. Commonly ax SpA progresses from sacral inflammation to progressive spine ankylosis over time. Since patients with early disease may not show x-ray abnormalities related to SpA, new technologies such as MRI are increasingly being utilized. The Assessment of SpondyloArthritis international Society (ASAS) recently created a classification system for ax SpA based on whether patients meet clinical criteria or imaging criteria. Patients meeting the ASAS criteria for ax SpA without evidence of sacroiliitis on x-ray are classified as having nr-ax SpA. With the advent of new consensus based criteria that allow earlier identification of patients with ax SpA, before significant x-ray abnormalities develop, earlier therapeutic intervention may potentially impact the natural history of the disease by shutting down early inflammation, as this may be the forerunner of irreversible bony ankylosis. In several recent studies, anti-tumor necrosis factor (TNF) agents, including ETN, demonstrated efficacy in patients with nr-ax SpA. However, additional long-term data are needed, and little is known about the effects of ETN withdrawal in subjects who have achieved a significant clinical response.

In a small trial (ESTHER) of etanercept-treated patients who had achieved an ASAS partial remission after 48 weeks of etanercept treatment, 13 with nr-ax SpA were withdrawn from therapy. The flare rate in year 2 was 69%, and the mean time to flare was 24.4 weeks. Retreatment with etanercept showed an improvement in all clinical (BASDAI, ASDAS, CRP) and imaging (MRI SIJ, MRI spine, MRI enthesitis) variables. Only a portion of the subjects re-established remission status (56% ASAS remission; 44% MRI remission; 33% MRI plus ASAS remission).

In study B1801031, patients with nr-ax SpA given a 12 week course of ETN had significantly reduced clinical signs and symptoms as well as SIJ and spinal inflammation on MRI as compared to patients receiving placebo. An open-label extension is currently underway to examine long-term efficacy and safety.

Little is known about the effects of ETN withdrawal in subjects who have achieved a significant clinical response. A small study with a mixture of AS and nr-ax SpA patients having achieved a significant clinical response showed that approximately 75-80% of subjects had relapses after 2 years. After retreatment, only about a third recovered the level of clinical response they had achieved at the time of withdrawal. However, firm conclusions regarding the effects of withdrawal and retreatment could not be drawn due to the low numbers of patients in the study.

The proposed study is a followup of this small pilot study that will further our understanding of the benefits and risks of ETN withdrawal in patients who have achieved a significant clinical response. Much is known already from B1801031 about relapse rates of those achieving remission and continuing on ETN, therefore an open-label study estimating the relapse rates in such patients withdrawn from ETN is planned.

Overall, the benefits of ETN administration in patients with nr-ax SpA are expected to include reduced disease activity, including less pain, reduced inflammation of the SIJ, and improved physical function. Based on the safety experience from the B1801031 study combined with the long-term safety data and post-marketing safety experience in AS, an acceptable safety profile is expected in nr-ax SpA patients treated with ETN. Consequently, the risk-benefit balance of ETN for the treatment of nr-ax SpA is considered to be positive in patients who have high disease activity despite treatment with NSAIDs. Furthermore, the risk benefit may be more favorable in patients with objective evidence of inflammation, ie, those who have high CRP and/or MRI inflammation. The proposed study will further our understanding of the benefits and risks of ETN withdrawal in patients who have achieved a significant clinical response.

The dosing regimen chosen for this study is in agreement with the recommended dosage for AS in adults ages 18 or older.

Complete information for this compound may be found in the single reference safety document (SRSD), which for this study is the Investigator Brochure (IB).

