\*\*Subjects in this study cannot meet the criteria based on the second bullet (since defined radiographic sacroiliitis is an exclusion criterion). In order to meet the imaging criteria for ASAS, subjects must have positive sacroiliitis on MRI based on readings performed by the central imaging vendor. This criterion **cannot** be based on local MRI evaluation or historical MRIs.

If a subject has negative sacroiliitis on MRI, then they must have positive HLA-B27 plus 2 SpA features. Conversely, if a subject is HLA-B27 negative, then they must have positive sacroiliitis on MRI and at least 1 SpA feature. (See flowchart in [Appendix 6](#)).

The SpA features are listed below and defined in [Appendix 4](#).

- Inflammatory back pain;
  - Arthritis;
  - Enthesitis (heel);
  - Uveitis;
  - Dactylitis;
  - Psoriasis;
  - Crohn's/ Colitis;
  - Good response to NSAIDs;
  - Family history of SpA;
  - HLA-B27;
  - Elevated hsCRP.
6. Subjects must have positive MRI findings (active inflammation on MRI highly suggestive of sacroiliitis associated with SpA) and/or positive hsCRP (defined as hsCRP >3 mg/l).
  7. Active symptoms defined by an ASDAS CRP greater than or equal to 2.1 at the screening visit.
  8. Back pain with a less than favorable response to current intake of an NSAID at the optimal tolerated dose as determined by the investigator. Subjects must have experienced less than favorable response to at least 2 NSAIDs (including the current one) taken separately at the optimal tolerated dose with a total combined duration of >4 weeks.
  9. Subject must be taking a stable dose of an NSAID for at least 14 days before the first dose.
  10. Female or male 18 years or older (20 or older if required by local regulations) but less than 50 at the time of consent.

11. In the opinion of the investigator, subject is reasonable candidate for treatment with ETN.
12. No contraindication to MRI examination (metal implants or inability to lie flat for 30-60 minutes for example).
13. Negative serum pregnancy test performed at screening, negative urine pregnancy test performed prior to the first dose and negative serum pregnancy test collected for analysis prior to the first dose.
14. Ability to self-inject investigational product or have a designee who can do so.
15. Ability to store injectable investigational product under refrigerated conditions.
16. Demonstrated an adequate screening for tuberculosis (TB) in accordance with local country guidelines.

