## Appendix 6. ASAS Eligibility Flowchart

# ASAS Eligibility Flowchart

- Duration of symptoms >3months and < 5 years at time of consent.
- Diagnosis of axial spondyloarthritis, as defined by ASAS criteria.
- In order to meet imaging criteria for ASAS, subjects must have positive Sacroiliitis on MRI based on readings performed at BioClinica. Subjects negative for Sacroiliitis on MRI must have positive HLA-B27 plus 2 SpA features (one SpA feature must be elevated hsCRP). Conversely, subjects that are HLA-B27 negative must have positive Sacroiliitis on MRI plus 1 SpA feature.

Please note this is a portion of the overall eligibility criteria and these criteria alone do not make the subjects eligible for randomization! Subjects must meet eligibility requirements for radiological sacroiliitis. They are not eligible if the centrally read x-ray of the SI joint meets modified NY criteria.

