6. ANALYSES AND SUMMARIES

6.1. Primary Endpoint(s)

6.1.1. ASDAS flare

6.1.1.1. Primary Analysis

Endpoint: ASDAS flare (ASDAS ESR greater than or equal to 2.1).

- Analysis time points: Period 2 (over entire period).
- Analysis population: Period 2 FAS.
- method of imputation for missing data: LOCF.
- Primary analysis methodology: Descriptive summary only of proportion flared at each period 2 visit.

Reporting results:

- Descriptive: proportions (n/N) and 95% Confidence interval) at each period 2 visit.

- Supporting objective and Decision rule: Primary Objective.

Additional analyses for primary endpoint

- Method of imputation for missing data: None .
- Analysis methodology: Kaplan Meier estimate of time to flare and Cox proportional hazards model for evaluation of covariates and estimation of hazard compared to prior study B1801031 which had no withdrawal of treatment.
- Supporting objective and Decision rule: Primary Objective.
- Covariates used (Cox model): Covariates for the Cox regression model of time to flare will include, in addition to study (B1801031 vs B1801381), age, sex, geographic region, baseline CRP (normal vs. high), baseline MRI status (negative vs. Positive), disease duration, prior NSAID response (good vs. not) plus ASDAS values at weeks 12 and 24 or, in a separate model, sustained ASDAS inactive disease in period 1, defined as ASDAS ESR<1.3 at Week 12 or Week 16 (where ASDAS may not be greater than 2.1 at either time point) and at Week 24. Binary variables with small frequencies in either study will not be included in the Cox regression model.

Reporting results:

- Estimation:

Kaplan-Meier estimates of 25%, median and 75% survival and 95% confidence intervals.
Cox model based hazard ratio estimates for covariates and study.
- Tables: Present table with just HR and CI for “study” for 4 models:
 1. study only
 2. study plus baseline variables
 3. study plus baseline variables plus ASDAS continuous at 2 times
 4. study plus baseline variables plus sustained ASDAS remission
- Figures:

Kaplan Meir plots showing both studies flare events.

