6.4. Subset Analyses

In addition to summarization of the overall population, the ASDAS flare endpoint will be summarized for key demographic and baseline disease characteristics for the B1801381 population. For each demographic and disease characteristic subgroup, the response in each subgroup category will be presented (responder count, group size, and response percent). In addition Cox regression models with factors for study, subgroup and study by subgroup interaction will be fit, separately for each subgroup. Results will be summarized with hazard ratios and 95% confidence intervals. The subgroups to be included are:

- Sex (Male, Female)
- Race (White, Non-White)
- Age category (<40 years, >=40 years)

- Weight (<70kg, ≥70 kg)
- Baseline hs-CRP status (High, Normal)
- HLA-B27 status (Positive, Negative)
- Concomitant use of DMARDs at Baseline (Yes, No)
- MRI sacroiliitis classification at Screening (Positive, Negative)
- Both positive MRI and elevated baseline hs-CRP (Yes/No)
- Baseline/screening MRI SIJ SPARCC score >2 (yes, no)
- History of IBD at Screening (Yes, No)
- History of uveitis at Screening (Yes, No)
- Disease duration <2 years (Yes, No).

Before the final model is determined, data patterns will be examined for feasibility issues, including highly correlated predictors and small cell size in subgroups. Adjustments will be made as necessary to address any such issues.

To support the interpretation of the primary analysis the following analysis will be performed:

- Sustained period one responders vs. responders at week 24 only.

An additional summary evaluating flare rates in those subjects who met the entry criteria only at week 24 and those who were sustained responders [subjects who, in addition to ASDAS ESR <1.3 at week 24, also have ASDAS ESR <1.3 at Week 12 or Week 16 (where ASDAS may not be greater than 2.1 at either time point)] will be provided. Populations and methodology will be applied as above.

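### The entry rule ties MRI-negative status to HLA-B27 positivity and high CRP, so the single-factor flare rows in SAP 6.4, and the MRI hazard ratio in models that omit HLA-B27, can mislead

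*Protocol*

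**What the plan says.** Protocol 1.2, on the risk-benefit of treating nr-ax SpA with etanercept: "the risk benefit may be more favorable in patients with objective evidence of inflammation, ie, those who have high CRP and/or MRI inflammation".

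Protocol 4.1, criterion 5: "If a subject has negative sacroiliitis on MRI, then they must have positive HLA-B27 plus 2 SpA features". Criterion 6: "Subjects must have positive MRI findings (active inflammation on MRI highly suggestive of sacroiliitis associated with SpA) and/or positive hsCRP", with the hsCRP threshold set at 3 mg/L. Appendix 6 puts the two together for MRI-negative subjects, adding that "one SpA feature must be elevated hsCRP".

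SAP 6.4 gives flare count, group size and percent in B1801381 for each of a list of subgroups. MRI status, hs-CRP status and HLA-B27 status are separate items. The list also has one combined item, "Both positive MRI and elevated baseline hs-CRP (Yes/No". The Cox models there hold study, subgroup and their interaction, and "will be fit, separately for each subgroup".

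SAP 6.1.1.1 lists the covariates for its adjusted Cox models. They include "baseline CRP (normal vs. high), baseline MRI status (negative vs. Positive", but not HLA-B27. The results section there calls for hazard ratios for the covariates as well as for study.

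**The concern.** The entry rule removes part of the MRI-by-CRP-by-HLA-B27 table before the first dose. The MRI-negative group is uniformly CRP-high and HLA-B27 positive at screening, while the MRI-positive group is mixed on both. A single-factor MRI row therefore compares groups that differ by design on two other possible predictors of flare. The CRP and HLA-B27 rows have the same fault the other way round, because every CRP-normal subject and every HLA-B27-negative subject at screening is MRI positive.

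The combined item does not repair this. Its No level pools MRI-positive/CRP-normal with MRI-negative/CRP-high subjects. At stake is the reading of supportive tables: MRI inflammation could look harmless, or even protective, after withdrawal when it is not. A larger sample would not remove this.

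**Working it through.** **Planning figures.** The documents give no figure for these subgroup or covariate analyses. The two planning numbers used below, 96 subjects entering Period 2 and 70% flare (Protocol 9.1), do reproduce the stated precision: 1.96 × √(0.70 × 0.30 / 96) = 0.092, or 0.096 by the exact method, against a stated half-width of about 10%.

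**Step 1: what entry allows.** Criterion 5 needs MRI positive or HLA-B27 positive. Criterion 6 needs MRI positive or hsCRP above 3 mg/L. Of the eight MRI × HLA-B27 × CRP combinations, all four MRI-positive ones pass. Only one MRI-negative combination passes: HLA-B27 positive with high CRP.

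**Step 2: assumptions (none is in the documents).** 25% of Period 2 entrants are MRI negative. Among MRI positives, 50% are CRP-high and 65% HLA-B27 positive, independently. The true MRI hazard ratio (HR) is 1.5. Flare times are exponential, scaled to 70% flare at 40 weeks.

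**Step 3: apparent MRI hazard ratio.** With h for true HRs and p for shares among MRI positives, the unadjusted ratio at the start of follow-up is

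h_MRI × (p_CRP·h_CRP + 1 − p_CRP)/h_CRP × (p_B27·h_B27 + 1 − p_B27)/h_B27.

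Adjusting for CRP removes the middle factor. For CRP HR 2.0 and HLA-B27 HR 1.3, the unadjusted value is 1.5 × 1.5/2.0 × 1.195/1.3 = 1.03, and the CRP-adjusted value is 1.5 × 1.195/1.3 = 1.38. The simulated columns are Cox fits on 40,000 subjects.

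| CRP HR | HLA-B27 HR | Unadjusted: formula | Unadjusted: simulated | CRP-adjusted: formula | CRP-adjusted: simulated |
|---|---|---|---|---|---|
| 1.5 | 1.0 | 1.25 | 1.24 | 1.50 | 1.53 |
| 1.5 | 1.3 | 1.15 | 1.13 | 1.38 | 1.40 |
| 2.0 | 1.3 | 1.03 | 0.99 | 1.38 | 1.40 |
| 2.0 | 1.5 | 0.99 | 0.94 | 1.33 | 1.33 |

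With CRP and HLA-B27 both in the model, the simulated MRI HR is 1.53 to 1.54 in every row. Simulation error is about ±0.04: 28,000 flares give a log-HR standard error of 1/√(28,000 × 0.25 × 0.75) = 0.014. The unadjusted fits mostly fall below the formula because the mixed MRI-positive group loses its high-risk members first. Smaller simulations of the last row gave 0.89.

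**Step 4: the flare table itself.** Take the third row, with baseline cumulative hazard 0.48 at 40 weeks.
- MRI negative: 1 − exp(−0.48 × 2.0 × 1.3) = 71.3%.
- MRI positive: the four cells have relative hazards 1.5, 1.95, 3.0 and 3.9, weights 0.175, 0.325, 0.175 and 0.325, and flare 51.3%, 60.8%, 76.3% and 84.6%. The weighted mean is 69.6%.
- Overall: 0.75 × 69.6 + 0.25 × 71.3 = 70.0%.

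A true 1.5-fold effect is shown slightly reversed.

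**Step 5: the other rows.** Now assume 50% MRI negative, 50% CRP-high and 60% HLA-B27 positive among MRI positives, MRI HR 2.0, CRP HR 1.5 and no HLA-B27 effect. The mean relative hazard is (0.50 × 1.5 + 0.25 × 3.0)/0.75 = 2.0 in CRP-high subjects and 2.0 in CRP-normal subjects. The true CRP ratio of 1.5 disappears (simulated 0.95). In the same scenario HLA-B27, with no effect, shows a simulated HR of 0.74.

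**Step 6: no true MRI effect.** With the Step 2 shares, CRP HR 1.5 and HLA-B27 HR 1.3, the apparent MRI HR is 1.0 × 0.833 × 0.919 = 0.77 (simulated 0.76).

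**Step 7: precision.** With 0.70 × 96 = 67 flares split 25:75, the log-HR standard error is 1/√(67.2 × 0.25 × 0.75) = 0.28, so an HR of 1.5 has a 95% interval of 0.86 to 2.61. Within CRP-high, HLA-B27-positive subjects there are 96 × 0.75 × 0.50 × 0.65 = 23 MRI positives against 24 MRI negatives. At 70% flare the interval is 0.76 to 2.96.

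**The case against.** The plan does more than a quick reading suggests. A reader might infer that MRI and CRP are only ever examined singly and that HLA-B27 is in no Cox model. Neither is so: models 2 to 4 enter MRI and CRP together, SAP 6.4 has a combined item, and HLA-B27 has its own model there. Joint entry removes the CRP part of the problem, so those models attenuate the MRI effect and do not reverse it in the table above. Their specified table shows only the study hazard ratio.

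A reader might also infer that the rationale asks whether MRI or CRP tells us who can stop treatment. The quoted sentence is about the risk-benefit of giving etanercept, and no objective concerns predictors of flare. Nor do the documents support extending the point to the between-study comparison. With an assumed reference study of the same mix and a study HR of 5, the MRI interaction HR came out at 0.98, 0.98, 0.94 and 0.94 against a true 1.0, so a shared imbalance largely cancels. Whether the B1801031 subjects have the same mix is not stated.

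Finally, the bias is modest beside the sampling error in Step 7, every share and effect is assumed, and SAP 6.4 promises to look for correlated predictors and small cells.

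Most of this stands and limits the point. What remains is the descriptive flare rows and the MRI hazard ratio among the covariates. The promised check names no remedy, and a model holding only one of the three factors cannot reveal their dependence.

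**Conclusion.** The point holds for supportive analyses only, as an improvement to consider. The single-factor MRI, CRP and HLA-B27 flare rows for B1801381 are confounded by the entry rule. If CRP or HLA-B27 predicts flare, a true MRI hazard ratio of 1.5 appears as about 1.2 to 0.9 on the assumed shares. In models 2 to 4 only the MRI hazard ratio is affected, at about 1.3 to 1.4, and only if HLA-B27 predicts flare. If neither factor predicts flare, the MRI contrast is unbiased.

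The HLA-B27 dependence is complete, since HLA-B27 is tested only at screening. The CRP dependence is complete only at screening: SAP 3.4 takes the last screening or baseline value, and the SAP does not define high, so some MRI-negative subjects may be classed CRP-normal.

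The primary flare proportion and the Kaplan-Meier estimates are unaffected. No problem is shown for the study hazard ratio or the study-by-subgroup interaction.

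**What to change.** - **SAP 6.1.1.1:** add HLA-B27 to the baseline covariates of models 2 to 4. It is already collected, and SAP 6.4 expects it in both studies. The existing rule on sparse binary variables would still apply.
- **SAP 6.4, combined item:** replace the Yes/No MRI/CRP factor with three levels (MRI positive/CRP high, MRI positive/CRP normal, MRI negative/CRP high), plus any subjects who are MRI negative and CRP normal by the baseline value. Give flare n/N for each level, split by HLA-B27 where MRI is positive. State the CRP cut that defines high.
- **SAP 6.4, single-factor rows:** keep them, with a note that the MRI and CRP rows are confounded by the entry rule. Add the MRI contrast within CRP-high, HLA-B27-positive subjects, labelled descriptive only.

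The cost is SAP wording, one extra model term and a re-cut table, with no new data. The downside is small cells and wide intervals: the restricted contrast has roughly 23 against 24 subjects on the assumed shares and cannot support a firm conclusion.
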